
Although these studies show resolution of metabolic complications, the studies suffer from small sample size, retrospective nature, lack of randomization, and lack of uniform medical management. A large prospective randomized study of subclinical hypercortisolism is needed to better define the optimal management of these patients and conclusively demonstrate the benefit of adrenalectomy or lack thereof. We hypothesize that operative treatment would reduce the risk of long term consequences, and propose a prospective randomized trial evaluating and comparing non-operative and operative management of subclinical hypercortisolism.

Proposed correlative studies include determination of optimal diagnostic test for subclinical hypercortisolism, improvement of patient quality of life with adrenalectomy, assessing the incidence and the risk of deep venous thrombosis, diagnostic capability of dermal thickness and subclinical hypercortisolism, the diagnostic capability of ultrasound of the skin and the ability to predict resolution of subclinical hypercortisolism, rate of malignant adrenal neoplasm or tumor growth, the ability of bone turnover markers to predict resolution of osteoporosis, and the determination of whether FDG PET/CT scan is diagnostic of subclinical hypercortisolism.

Although surgery may improve the metabolic consequences of subclinical hypercortisolism, the importance of assessing the health-related quality of life of patients cannot be underestimated. As previously described, Iacobone et. al. (10) retrospectively compared patients who underwent an adrenalectomy (n=20) and those who opted for conservative management (n=15). In addition to assessing the metabolic consequences between the two groups, Iacobone et. al. assessed their quality of life with the SF-36 Health Survey. The SF-36 is a validated self-administered questionnaire with 2 components: the Physical Component Summary (PCS) and the Mental Component Summary (MCS). The two components correlate with the patient's physical and mental subjective perception of quality of life, respectively. In the operative group the SF-36 MCS score improved from a baseline score of 43.8 ± 11.8 to 54.1 ± 10.1 ($p=0.003$) after adrenalectomy. Similarly, the SF-36 PCS score improved from a baseline score of 50.9 ± 7.3 to 56.7 ± 7.3 ($p=0.0016$) after adrenalectomy. The baseline and at final follow up for patients that had opted for observation were not significantly different. A comparison of patients at final follow up who underwent adrenalectomy and patients who opted for observation showed a significant difference in quality of life scores: SF-36 MCS 54.1 ± 10.1 vs. 44.9 ± 12.4 ($p<0.05$), and SF-36 PCS 56.7 ± 7.3 vs. 50.5 ± 9.4 ($p<0.05$), respectively (10). However, since the patients in this study were not randomized and opted either for surgery or observation, there is an inherent selection bias. A correlative study with a randomized population would be helpful in determining the health-related quality of life score and potential improvement after adrenalectomy.

In order to better assess the quality of life impact on patients with subclinical hypercortisolism, we plan to use a validated Cushing's syndrome (CS) specific questionnaire (Appendix A) and correlate that questionnaire with the generic SF-36 questionnaire (Appendix C). The CS specific questionnaire has been previously validated in a cohort of 125 patients with chronic exposure to hypercortisolism. The observational cross-sectional study consisted of patients with pituitary-dependent (n=107) and adrenal-dependent CS (n=18). A subset of these patients (n=26) had an elevated urine free cortisol and clinical evidence of ongoing hypercortisolism confirmed by an endocrinologist. A comparison of these patients to a subset of patients without hypercortisolism (n=60) revealed that ongoing hypercortisolism is associated with a worse score and quality of life (44 ± 22 vs. 56 ± 21 , $p=0.004$) (26). This Cushing's specific questionnaire may be more specific in identifying the psychological impact of subclinical hypercortisolism and be helpful in assessing the impact of adrenalectomy.

The risk of venous thromboembolism (VTE) in patients with subclinical hypercortisolism is currently unknown and an extensive examination of the literature did not reveal any published studies. However, the risk of venous thromboembolism in patients with CS has been documented and reported to be more than 10-fold higher compared to the general population (27). The incidence of VTE prior to surgery in patients with CS has been documented to be between 2.5 to 3.1 per 1000 person-years. In the general population, the estimated incidence of VTE is 1 to 2 per 1000 person-years, which indicates that there is a slightly higher incidence of VTE in patients with CS. However, since the majority of patients affected by CS are women and the mean age is 40 years of age, an appropriate comparison would take these demographics into account. A demographically matched cohort reveals that the reported incidence rate is 0.27 per 1000 person-years, which shows that the incidence of VTE is much higher in patients with CS (28). Stuijver et. al. (29) published one of the largest retrospective studies examining Cushing's syndrome and VTE. The study included 473 patients with a diagnosis of CS. A subset of these

patients (n=113) were diagnosed with ACTH-independent CS. Consistent with other studies, the cohort's average age was 43.5 (range 19 to 79) and was largely female (89.4%). The incidence rate of VTE prior to treatment in this cohort was 15.2 (95% CI 6.3-36.6) (29). The mechanism is believed to be increased production of procoagulant factors and activation of the coagulation cascade. Although the pathophysiology of increased production is not fully understood, there have been *in vitro* studies showing the direct effect of glucocorticoids on these factors (27). Given the increased risk of VTE in CS and the possible role of glucocorticoids in promoting a hypercoagulable state, we propose assessing the risk of VTE in patients with subclinical hypercortisolism with preoperative and postoperative bilateral lower extremity duplex.

As documented previously, osteoporosis has a prevalence of 30% in patients with subclinical hypercortisolism (10) and a comparison of patients with adrenal incidentaloma and subclinical hypercortisolism reveals a significantly lower bone mineral density, higher fracture prevalence, and spinal deformity. Fractures and spinal deformity were also significantly associated with subclinical hypercortisolism (20). Given these findings, it is important to assess the beneficial effects of adrenalectomy for these patients.

As previously described, overt physical signs excludes the diagnosis of subclinical hypercortisolism. The classical cutaneous manifestations of Cushing's syndrome such as facial plethora, acne, purpura, cutaneous atrophy, hirsutism, vellous hypertrichosis, and wide purplish striae over the abdomen, flanks, and upper arms are not identified (32). Although not clinically identifiable, the cutaneous effects of glucocorticoids may be detectable by measuring the epidermal and dermal thickness of skin. A study by Lehmann et. al. demonstrated that topical application of clobetasol propionate to the forearms of 3 volunteers for 6 weeks resulted in a 59% decrease in viable epidermal thickness, and flattening of the dermal-epidermal junction (33). Whether the mildly elevated levels of cortisol found in subclinical hypercortisolism lead to histological changes has not been explored. We propose to obtain a skin biopsy from the site of the incision and determine whether there have been histological changes associated with the mildly elevated cortisol levels and to see whether this correlates with the diagnosis of subclinical hypercortisolism. The skin biopsy would not lead to new incisions and/or scars and would not affect the healing of the wound.

Weight gain and obesity is very common in patients with subclinical hypercortisolism. As previously stated, overweight and/or obesity has a prevalence of 19 to 75% in patients with subclinical hypercortisolism (8, 10, 12-14). Commonly in CS, patients have central obesity with fat deposition in the abdomen, mediastinum, face and neck (32). This type of fat distribution has been tested noninvasively by ultrasound. Schou et. al. (34) assessed the changes in fat distribution noninvasively by ultrasound in asthmatic children who were given a short course of prednisolone. Twenty children participated in a double-blinded, randomized, placebo-controlled crossover trial. One group of children (n=10) received 5 mg of prednisolone daily (active arm) for one week, while the other group of children (n=10) received placebo for one week. At days 1 and 7, ultrasound measurements of the cutis and subcutis were done at three locations: the abdomen, the volar arm, and the thigh. The total thickness of the cutis and subcutis in the thigh significantly decreased in treatment group versus the placebo group (-0.28 ± 0.15 vs. 0.07 ± 0.14 mm, $p=0.04$). The volar arm and the abdomen locations did not show a significant change between the treatment and placebo group. There was a significant change in the treatment group when comparing the total thickness of the cutis and subcutis of the abdomen versus the thigh

Abbreviated Title: Subclinical Hypercortisolism

Version Date: 12/19/2016

(0.23 ± 0.16 vs. -0.28 ± 0.15 mm, $p=0.03$) and the total thickness of the cutis and subcutis of the abdomen versus the forearm (0.23 ± 0.16 vs. -0.15 ± 0.09 mm, $p=0.05$). These findings would be consistent with the glucocorticoid induced effects in central and peripheral fat distribution (34). This noninvasive test could potentially be utilized in patients with subclinical hypercortisolism as a diagnostic tool and to identify the resolution of subclinical hypercortisolism postoperatively. We will correlate the changes in subcutaneous fat distribution in patients who undergo adrenalectomy.

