1. INTRODUCTION

1.1 STUDY OBJECTIVES

1.1.1 Primary Objective

- To determine whether unilateral adrenalectomy in patients diagnosed with subclinical hypercortisolism and an adrenal neoplasm results in normalization and/or improvement of hypertension as assessed by reduction in pharmacotherapy and/or normalization of blood pressure (systolic pressure ≤ 140 and diastolic pressure ≤ 90), diabetes as assessed by reduction or elimination of pharmacotherapy and/or improvement in A₁C to $< 6.5\%$, osteoporosis by increase in bone formation markers indicative of increased bone formation, hypercholesterolemia as assessed by a reduction or elimination of pharmacotherapy and/or reduction in LDL levels to risk-stratified goal levels as defined by ATP III, and/or overweight or obesity as assessed by a 10 percent reduction in weight at 6 months.

1.1.2 Secondary Objectives:

- To determine the risk of primary adrenal malignancy in patients with subclinical hypercortisolism and adrenal mass less than 5 cm.
- To determine whether FDG PET/CT scan is diagnostic of subclinical hypercortisolism.
- To determine the optimal diagnostic test for subclinical hypercortisolism.
- To determine whether patients show an improvement in quality of life after adrenalectomy compared to medical therapy.
- To determine whether patients have an increased risk of deep venous thrombosis with subclinical hypercortisolism, regardless of treatment.
- To determine whether dermal thickness is diagnostic of subclinical hypercortisolism.
- To determine whether ultrasound of the skin is diagnostic and is able to show resolution of subclinical hypercortisolism after adrenalectomy.

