2.5.7.12 Fasting Triglyceride, total cholesterol, LDL, HDL levels

3 STUDY IMPLEMENTATION

3.1 STUDY DESIGN

This is a prospective randomized study of individuals with an adrenal mass less than or equal to 5 cm with biochemically confirmed hypercortisolism (2 out of 3: DST >3 mmol/l, elevated urine free cortisol, and/or morning ACTH <2.2 pmol/l) without overt clinical signs and/or symptoms (facial plethora, easy bruising, violaceous striae, and/or proximal muscle weakness) of excess cortisol. Individuals will undergo a clinical work up for an adrenal mass including laboratory and radiological studies (see below). Patients diagnosed with subclinical hypercortisolism and an adrenal mass less than 5 cm will be randomly assigned to either the non-operative or operative arm of the study. In patients found to have bilateral adrenal masses, the larger of the two masses will be treated as the adrenal lesion responsible for subclinical hypercortisolism. These patients with bilateral adrenal masses will be randomly assigned to either the non-operative or operative arm of the study. The responsible lesion will be adrenal mass that will be removed with a unilateral adrenalectomy or monitored. For patients in the non-operative or medical treatment-only arm, baseline evaluation will be undertaken, as well as follow up and re-evaluation every 3 months for 6 months, after which they will crossover to the operative arm and undergo an adrenalectomy. If a patient develops overt signs and symptoms of cortisol excess during the 6 months of observation, the tumor grows after enrollment during the 6 months of observation or 6 months have elapsed, the patient will cross over to the operative arm, and undergo an adrenalectomy. Worsening of metabolic complications will not be an indication for crossover. Patients after crossing over to the operative arm will have follow up every 3, 6, 9, and 12 months for the first year, six month follow up thereafter for the second year, and yearly follow up thereafter for three years. For a patient in the operative arm, the patient will undergo baseline evaluation, adrenalectomy, and follow up every 3, 6, 9, and 12 months for the first year, six month follow up thereafter for the second year, and yearly follow up thereafter for three years. At each follow-up visit, the patient will undergo repeat radiological and laboratory evaluation (see [Table 1](#)). Uniformity of medical management will be ensured by coordinating with primary care physicians, endocrinologists and the utilization of national guidelines in treating the metabolic manifestations and consequences of subclinical hypercortisolism.

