
Table 1

Abbreviated Title: Subclinical Hypercortisolism**Version Date: 12/19/2016****3.2 QUESTIONNAIRES**

The questionnaires to be utilized include the generic SF-36 and the Cushing specific quality of life questionnaire (26). The questionnaires will assess the patient's quality of life preoperatively and postoperatively. The questionnaires will take approximately ten minutes to complete. The SF-36 form will be given first, and the Cushing's specific quality of life questionnaire will follow. The topics will address general health and wellbeing. After the questionnaires are collected and entered into a computer database, the data will be shredded.

*Abbreviated Title: Subclinical Hypercortisolism**Version Date: 12/19/2016***3.3 STUDY CALENDAR****3.3.1 Operative Arm**

Baseline and Follow-up Testing for Operative Arm					
Test	Baseline evaluation (MO)	3 monthly evaluation (M3)	3 monthly evaluation (M6, M9)	6 monthly evaluation (M12, M18)	12 monthly evaluation (M24, M36, M48, M60)
QoL Questionnaire	x	x		x	
CT adrenal	x				
FDG PET/CT scan	x				
DEXA	x			x	x
Duplex	x	x			
Vertebral (X-rays) morphometry and body composition	x	x	x		
Skin ultrasound	x	x	x	x	x
CBC	x	x	x	x	x
Chemistries	x	x	x	x	x
PT/PTT/INR	x				
Renin/PAC	x				
24 hour urine free cortisol	x	x			
midnight serum/salivary cortisol	x	x			
baseline serum cortisol	x	x			
DST	x	x			
plasma ACTH	x	x			
serum fractionated plasma normetanephrines and metanephrines	x				
24-hour urinary epinephrine, dopamine, norepinephrine, and fractionated normetanephrines and metanephrines	x				
DHEA	x	x	x	x	
Urinary 17 ketosteroids	x	x	x	x	x
testosterone	x	x			
24 hour urinary calcium, phosphorous,	x	x	x	x	x

*Abbreviated Title: Subclinical Hypercortisolism**Version Date: 12/19/2016*

Baseline and Follow-up Testing for Operative Arm					
Test	Baseline evaluation (MO)	3 monthly evaluation (M3)	3 monthly evaluation (M6, M9)	6 monthly evaluation (M12, M18)	12 monthly evaluation (M24, M36, M48, M60)
amino acid random urine					
25-OH Vitamin D Level	x	x	x	x	x
PTH	x	x			
fasting glucose	x	x	x	x	x
A ₁ C	x	x	x	x	x
Triglyceride, total LDL, HDL levels	x	x	x	x	x
NIH Advanced Directives Form¹	x				

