3.3.2 Non-Operative Arm

Baseline and Follow-up Testing for Non-Operative Arm						
Test	Baseline evaluation (MO)	Preop 3 monthly evaluation (M3, M6)	3 monthly evaluation (M9)	3 monthly evaluation (M12, M15)	6 monthly evaluation (M18, M24)	12 monthly evaluation (M30, M42, M54, M66)
QoL Questionnaire	x	x	x		x	
CT adrenal	x	x				
FDG PET/CT scan	x					
DEXA	x				x	x
Duplex	x	x	x			
Vertebral (X-rays) morphometry and body composition	x		x	x		
Skin ultrasound	x	x	x	x	x	x
CBC	x	x	x	x	x	x
Chemistries	x	x	x	x	x	x
PT/PTT/INR	x					
Renin/PAC	x					

*Abbreviated Title: Subclinical Hypercortisolism**Version Date: 12/19/2016*

Baseline and Follow-up Testing for Non-Operative Arm						
Test	Baseline evaluation (MO)	Preop 3 monthly evaluation (M3, M6)	3 monthly evaluation (M9)	3 monthly evaluation (M12, M15)	6 monthly evaluation (M18, M24)	12 monthly evaluation (M30, M42, M54, M66)
24 hour urine free cortisol	x	x	x			
midnight serum/salivary cortisol	x	x	x			
baseline serum cortisol	x	x	x			
DST	x	x	x			
plasma ACTH	x	x	x			
serum fractionated plasma normetanephrines and metanephrines	x	x				
24-hour urinary epinephrine, dopamine, norepinephrine, and fractionated normetanephrines and metanephrines	x	x				
DHEA	x	x	x	x	x	
Urinary 17 ketosteroids	x	x	x	x	x	x
testosterone	x	x	x			
24 hour urinary calcium, phosphorous, amino acid random urine	x	x	x	x	x	x
25-OH Vitamin D Level	x	x	x	x	x	x
PTH	x	x	x			
fasting glucose	x	x	x	x	x	x
A ₁ C	x	x	x	x	x	x
Triglyceride, total LDL, HDL levels	x	x	x	x	x	x

Abbreviated Title: Subclinical Hypercortisolism

Version Date: 12/19/2016

Baseline and Follow-up Testing for Non-Operative Arm						
Test	Baseline evaluation (MO)	Preop 3 monthly evaluation (M3, M6)	3 monthly evaluation (M9)	3 monthly evaluation (M12, M15)	6 monthly evaluation (M18, M24)	12 monthly evaluation (M30, M42, M54, M66)
NIH Advanced Directives Form¹						

¹ As indicated in section 10.3, all subjects will be offered the opportunity to complete an NIH advanced directives form. This should be done preferably at baseline but can be done at any time during the study as long as the capacity to do so is retained. The completion of the form is strongly recommended, but is not required.

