7 STATISTICAL CONSIDERATIONS

The primary objective of this study is to determine if the use of unilateral adrenalectomy is associated with normalization and/or improvement of hypertension, diabetes, osteoporosis, hypercholesterolemia, and/or obesity compared to medical treatment-only arm.

Patients with subclinical hypercortisolism will be randomized to adrenalectomy or medical treatment as defined above and followed for 6 months. At the end of 6 months, the patients who were in the medical treatment-only arm will all be offered an adrenalectomy. Patients with subclinical hypercortisolism tend to have high prevalence of metabolic consequences, specifically hypertension, diabetes, obesity and/or osteoporosis.

To be conservative, the primary goal of this study will be to determine if the use of adrenalectomy is associated with 35% who have improvement vs. 5% who improve over 6 months without surgery as defined for any one or more of the following associated complications: hypertension, diabetes, osteoporosis, hypercholesterolemia, and/or obesity. With 31 patients per arm (62 total), there would be 80% power to detect a difference of this magnitude using a 0.05 significance level two-tailed Fisher's exact test.

For the potential 31 patients initially randomized to observation and then undergoing an adrenalectomy at 6 months, the level of MAP, systolic, and diastolic pressure at 6 months but just before surgery will be compared to these values in the potential 31 patients initially randomized to immediate adrenalectomy 6 months after surgery using a Wilcoxon rank sum test. In addition, in the patients initially randomized to observation the changes in MAP from baseline to 6 months of observation as well as the declines in systolic and diastolic pressure from 6 months of observation until 6 months after surgery will be compared with a Wilcoxon signed rank test. Other important continuous parameters such as change in weight, triglycerides, total, HDL and LDL cholesterol, A1c, fasting glucose, and bone density may also be compared within patients using Wilcoxon signed rank test.

Abbreviated Title: Subclinical Hypercortisolism

Version Date: 12/19/2016

It is expected that 15-20 eligible patients may be able to enroll on this trial per year. In order to enroll 62 evaluable patients, it is anticipated that 3-4 years would be required. In order to allow for a small number of inevaluable patients, the accrual ceiling will be set at 66 patients.

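### The skin-ultrasound resolution objective has one stated analysis, a correlation in operated patients with an unnamed variable; the randomised controls' scans at M0, M3 and M6 are given no role

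*Combined protocol and SAP*

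**What the plan says.** Section 1.1.2 lists as a secondary objective: "To determine whether ultrasound of the skin is diagnostic and is able to show resolution of subclinical hypercortisolism after adrenalectomy". Section 1.2 proposes the scan "as a diagnostic tool and to identify the resolution of subclinical hypercortisolism postoperatively" and then gives the only analysis statement for it: "We will correlate the changes in subcutaneous fat distribution in patients who undergo adrenalectomy". That sentence names no second variable, time point or comparator.

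Section 7 assigns no analysis to skin ultrasound. Its one between-arm comparison of continuous data is for blood pressure: controls at 6 months, just before surgery, against patients "initially randomized to immediate adrenalectomy 6 months after surgery using a Wilcoxon rank sum test". Its optional list of other parameters includes weight, lipids, glucose measures and "bone density may also be compared within patients using Wilcoxon signed rank test"; ultrasound is not on it.

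Section 2.5.3.6 fixes three measurement sites: abdomen, volar forearm and thigh. In both calendars (Sections 3.3.1 and 3.3.2) the row "Skin ultrasound" is marked in every column, including the non-operative column that begins "Preop 3 monthly evaluation (M3, M6". Under Section 3.1 the controls have "follow up and re-evaluation every 3 months for 6 months, after which they will crossover to the operative arm and undergo an adrenalectomy".

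**The concern.** To say that a scan shows resolution after surgery is to say that the change came from removing the cortisol excess. Patients who have all been operated on cannot show this by themselves. Their skin and fat thickness may also change through background weight change or altered drug treatment and, if the result is read as a before-after shift, through operator or equipment drift.

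The trial already collects the remedy, because randomised unoperated controls are scanned at the same nominal visits up to M6. The protocol applies this reasoning elsewhere: Section 1.2 criticises earlier studies for lack of randomisation and wants a randomised population for quality of life because of selection bias. The ultrasound evidence that it cites came from a placebo-controlled trial.

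Operated-only data may also hold little variation in the outcome. In the bilateral series cited in Section 1.2, hypercortisolism resolved in all surgical patients. If that recurs, few unresolved patients remain for a correlation to use.

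**Working it through.** **1. The plan's own figure.** The plan gives no power figure for ultrasound. Its primary figure is 80% power with 31 per arm, 35% vs 5%, two-tailed Fisher's exact test at 0.05. Summing Bin(a; 31, 0.35) × Bin(b; 31, 0.05) over all tables with Fisher p ≤ 0.05 gives 80.9% (78.8% at 30 per arm, 82.7% at 32). It reproduces.

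**2. What is collected before planned crossover (Sections 3.3.1 and 3.3.2).**

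| Visit | Ultrasound, operative | Ultrasound, non-operative | DST, UFC and ACTH, operative | DST, UFC and ACTH, non-operative |
|---|---|---|---|---|
| M0 | yes | yes | yes | yes |
| M3 | yes | yes | yes | yes |
| M6 | yes | yes | no | yes |

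M3 is therefore the one follow-up visit before planned crossover at which both arms have both the scan and the three cortisol tests.

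**3. Uniform drift.** Simulation: 3,000 trials, 31 per arm, normal changes with SD 1, no effect of surgery, the same mean shift in both arms. Entries are the percentage of trials with p < 0.05. The shift sizes are assumptions.

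| Shift (SD) | Signed rank, operated only | Spearman, operated only, unrelated variable | Rank sum between arms |
|---|---|---|---|
| 0 | 5 | 6 | 4 |
| 0.1 | 8 | 5 | 5 |
| 0.2 | 18 | 5 | 5 |
| 0.3 | 35 | 5 | 5 |
| 0.5 | 75 | 5 | 5 |
| 0.7 | 96 | 5 | 5 |

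Drift inflates a before-after test. It does not inflate a correlation, because adding a constant to every patient's change leaves the ranks as they were.

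**4. Shared weight change.** Let W be weight change and r its loading. Ultrasound change U = rW + √(1 − r²)e₁ and resolution variable H = rW + √(1 − r²)e₂, with e₁ and e₂ independent. U and H have no direct link, but their correlation is r². The loadings are assumptions.

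| r | r² | Spearman p < 0.05, n = 31 |
|---|---|---|
| 0.3 | 0.09 | 7% |
| 0.5 | 0.25 | 23% |
| 0.7 | 0.49 | 76% |

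**5. What the randomised comparison can detect.** Difference = (1.960 + 0.842) × SD × √(2/n). For n = 31 per arm: 2.802 × 0.254 = 0.71 SD. For 28 per arm it is 0.75 SD, and for 25 per arm 0.79 SD.

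**6. In millimetres.** The documents give no adult SD. The cited paediatric trial reports thigh changes of −0.28 ± 0.15 vs 0.07 ± 0.14 mm, a difference of 0.35 mm, without stating whether ± is an SD or a standard error. Power for 0.35 mm with 31 per arm:
- ± 0.15 is an SD: above 99%.
- ± 0.15 is a standard error with n = 10, so SD = 0.15 × √10 = 0.47: 83%.
- ± 0.15 is a standard error with n = 20, so SD = 0.15 × √20 = 0.67: 54%.

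These figures come from children treated for one week and indicate scale only.

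**The case against.** The strongest reply is that the plan says correlate, and a correlation in operated patients is the most direct way to ask whether ultrasound change tracks resolution. It is immune to uniform drift (step 3). This stands. The drift figures apply only if the result is read as a before-after change, which no section announces. Shared weight change is what threatens the correlation itself.

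Second, a sentence in a background section excludes nothing. A reader might infer that the controls are deliberately left out, or that any common change will be reported as resolution. The documents support neither; they show only that no controlled ultrasound analysis is written down. Nor are the measurement sites missing: Section 2.5.3.6 names three. What is missing is which site or contrast is main.

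Third, the randomised comparison has limits of its own.
- No blinding of the ultrasound readers is stated, so reading bias could differ by arm, and the 4 to 5% in step 3 assumes equal drift.
- M3 and M6 are nominal visits. Section 7 counts 6 months from surgery in one arm and 6 months of observation in the other.
- Weight loss caused by surgery stays in the between-arm difference. A reader might expect an abdomen-minus-thigh contrast to cancel weight change, but nothing in the documents shows that weight alters both sites equally. In the cited trial that contrast was significant only within the treated group; the one between-group difference was at the thigh.

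These points shape the remedy. They do not give the control scans a role in the plan.

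**Conclusion.** The concern holds in a limited form. The resolution half of the objective rests on one stated analysis, in operated patients, against an unnamed variable, while randomised unoperated scans at M0, M3 and M6 have no analytic role. Such data cannot separate surgery from background weight or drug change.

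Under the correlation as written, false-positive rates run from 7% to 76% over the assumed weight loadings. Under a before-after reading they run from 8% to 96% over assumed shifts of 0.1 to 0.7 SD. Neither range is a prediction for this trial, since the documents give no drift, loading or adult SD.

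A between-arm difference would show that surgery changes thickness. It would not by itself show that ultrasound tracks cortisol independently of weight. Only a secondary objective is affected.

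**What to change.** Add an ultrasound paragraph to Section 7:

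- **Main analysis:** between-arm difference, as randomised, in the M0-to-M6 change in thickness, adjusted for the M0 value and using control scans taken before crossover. State the time origin in each arm and how a control operated on before M6 (allowed by Section 3.1) is handled.
- **Sites:** report all three, with one site or site contrast named in advance as main.
- **Weight:** a sensitivity analysis adjusted for weight change, read with the caution that surgical weight loss may be part of the effect.
- **M3:** the same comparison, with the biochemical resolution variable named (from DST, UFC and ACTH). If its association with ultrasound change is estimated across both arms, include arm in the model; otherwise it largely restates the arm difference.
- **Supportive:** keep the operated-only correlation, against that same named variable.

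The cost is analysis wording and some analysis work, with no new scan, visit or patient. The controlled contrast covers M0 to M6 only, and later scans remain descriptive. Unless reader blinding is added, its absence should be reported as a limitation, together with the detectable difference of about 0.71 SD.
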